## 7.6. Long-term Follow-up for Disease Progression

Patient will be followed until disease progression or until they begin a new anti-cancer therapy, whichever happens first.

- Correlative studies (at time of disease progression)
- Bone marrow biopsy for response assessment (Section 7.3.8 and Section 7.9)
- Response Assessment (± 14 days), every 8 weeks (Section 7.9)

Following the Safety Follow-up Visit, patients with ongoing SAEs and study drug-related AEs will be followed for safety. If any SAEs or study drug-related AEs are ongoing after the Safety Follow-up Visit, follow-up with the patient will occur at least Q4W until resolution to baseline or stabilization of these events, unless the patient starts another anti-cancer treatment. Follow-up will stop when a patient begins another anti-cancer treatment. For patients who come off study treatment to receive a bone marrow transplant, follow-up for disease progression and collection of SOC bone marrow biopsy/aspirate results will continue until documented disease progression occurs.

The long-term care of the patient will remain the responsibility of his/her primary treating physician.

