## 7.7. Survival Follow-up

All patients who permanently discontinue all study treatment will be contacted during a clinic visit or by telephone to assess survival, and the commencement of new anti-cancer therapy following the last administration of study drug (if not documented previously). Patients will be contacted every 2 months (± 1 month) from the date of the Safety Follow-up Visit, until 3 years from the date that the last patient is enrolled in the study, unless there is full withdrawal of consent. The patient's primary physician or family may be contacted by the Investigator in order to obtain survival information in case the patient cannot be reached. For any patient who dies during this period, the cause of death must be reported to the Sponsor.

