**Duration of Response (DOR) for Patients with AML**: The duration of response is measured from the time measurement criteria are met for CR (including morphologic CR, CRMRD-, cCR, and mCR), CRi, CRh, PR, marrow CR, or MLFS, whichever is first recorded, until the first date that recurrent or progressive disease, or death with evidence of no disease progression is objectively documented. Those who are not observed to have recurrent or progressive disease or die with evidence of no disease progression during the trial active period will be censored at their last response assessment date with evidence of no progression/recurrence.

**Duration of CR for Patients with MDS**: The duration of CR for MDS patients is measured from the time measurement criteria are first met for CR until the first date that recurrent disease or death with evidence of no disease recurrence is objectively documented. Patients who are not observed to have recurrent disease or die with

evidence of no recurrence during the trial active period will be censored at their last response assessment date with evidence of no progression/recurrence.

Duration of Response for Patients with MDS: The DOR for MDS patients is measured from the time measurement criteria are first met for objective response (including CR, PR, marrow CR, and HI) as assessed by IWG MDS criteria (Cheson 2006) until the first date that recurrent disease or death with evidence of no disease recurrence is objectively documented. Those who are not observed to have recurrent disease or die with evidence of no recurrence during the trial active period will be censored at their last response assessment date with evidence of no progression/recurrence.

**Overall Survival (OS)**: The length of OS is measured from the date of study treatment initiation until the date of death from any cause. Those who are not observed to die during the trial active period will be censored at their last known alive date from survival follow-up.

**Progression-free Survival (PFS)**: The length of PFS is defined as the time from the date of study treatment initiation until the date of documented disease progression or relapse or death from any cause, whichever occurs first (Cheson 2003). Those who are not observed to have one of these events during the time the overall trial remains active will be censored at their last known progression-free follow-up date.

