**Event-free Survival (EFS)**: For AML, the length of EFS is defined as the time from the date of study treatment initiation until the date of documented disease progression, death from any cause, or treatment failure (defined as failure to achieve CR/CRi by Cycle 5 Day 1), whichever occurs first (Cheson 2003). For MDS, EFS is defined as the time from the date of study treatment initiation to transformation to AML or death from any cause, whichever occurs first. Those who are not observed to have one of these events during the time the overall trial remains active will be censored at their last known progression-free follow-up date.

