	more advanced MDS FAB subtype than pretreatment
Relapse after CR	At least 1 of the following:
or PR	Return to pretreatment bone marrow blast percentage
	
 
Decrement of ≥ 50% from maximum remission/response levels in granulocytes or platelets
 

	• Reduction in Hgb concentration by ≥ 1.5 g/dL or transfusion dependence d
Cytogenetic	Complete: Disappearance of chromosomal abnormality without appearance of
Response	new ones
	Partial: At least 50% reduction of the chromosomal abnormality
Disease	For patients with:
Progression	• Less than 5% blasts: ≥ 50 increase in blasts to > 5% blasts
	5%-10% blasts: ≥ 50% increase in blasts to > 10% blasts
	10%-20% blasts: ≥ 50% increase in blasts to > 20% blasts
	20%-30% blasts: ≥ 50% increase in blasts to > 30% blasts
	Any of the following:
	At least 50% decrement from maximum remission/response in granulocytes or platelets
	• Reduction in Hgb by ≥ 2 g/dL d
	Transfusion dependence d

Source: Cheson 2006

Abbreviations: CR = complete remission; FAB = myelodysplastic syndrome French-American-British classification; Hgb = hemoglobin; IWG = International Working Group; MDS = myelodysplastic syndrome; PR = partial remission.

- a. Dysplastic changes should consider the normal range of dysplastic changes
- b. Modification to IWG response criteria
- c. Transient cytopenias during repeated chemotherapy courses should not be considered as interrupting durability of response, as long as they recover to the improved counts of the previous course.
- d. Impact of anemia must be deemed disease-related and not due to study treatment.

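### MDS event-free survival is censored at the last progression-free date although progression is not an MDS event; the censoring is informative, with a bias whose size and net direction rest on assumptions

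*Protocol*

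**What the plan says.** Protocol Section 10 gives two EFS definitions. For AML the events are progression, death or treatment failure. The MDS definition is narrower: "For MDS, EFS is defined as the time from the date of study treatment initiation to transformation to AML or death from any cause". Progression short of AML is not an MDS event.

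A single censoring sentence then covers both diseases. It opens "Those who are not observed to have one of these events during the time the overall trial remains active will be censored" and sets the date: these patients "will be censored at their last known progression-free follow-up date". The PFS paragraph of the same section uses the same wording. Overall survival has its own rule: patients without an event "will be censored at their last known alive date from survival follow-up".

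Three other places matter:

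- Appendix B, Table 14-4, lets MDS progression occur without AML, for example "5%-10% blasts: ≥ 50% increase in blasts to > 10% blasts", or through a hemoglobin fall or transfusion dependence.
- Section 7.6 ends disease follow-up early: "Patient will be followed until disease progression or until they begin a new anti-cancer therapy, whichever happens first".
- Section 7.7 continues after treatment stops: "Patients will be contacted every 2 months", until 3 years after the last enrolment. These contacts cover survival, new anti-cancer therapy and cause of death. AML transformation is not listed.

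**The concern.** The censoring date belongs to a different event definition. It fits PFS and AML EFS, where progression is an event. It does not fit MDS EFS.

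Take two MDS patients who both progress without AML at month 6. One dies at month 10 and is an event at month 10. The other is alive without AML at month 30 and is censored at or before month 6. Whether the time after progression counts is decided by how that time ends, so the independent-censoring assumption of Kaplan-Meier fails by construction.

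EFS is a secondary endpoint (Section 2.2.2) in a population that includes the MDS Registrational Cohort. At stake are the reported curve, its median and its landmark rates.

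**Working it through.** The protocol states no EFS median, event number or power, so there is no figure to reproduce. The mechanism can be shown by hand; the size needs assumed hazards.

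**By hand.** Four patients progress without AML at month 6. Two die, at months 10 and 14; two are alive without AML at month 30.

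- Matching rule: 4 at risk at month 10, S = 3/4; 3 at risk at month 14, S = 3/4 × 2/3 = 1/2.
- Stated rule: the two survivors leave by month 6. 2 at risk at month 10, S = 1/2; 1 at risk at month 14, S = 0.

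**Follow-up from the protocol.** Enrolment takes 16 months (Section 3.7), survival follow-up runs to 3 years after the last enrolment (Sections 6.4 and 7.7), and the final analysis uses data to study discontinuation (Section 11). Potential follow-up is therefore 36 to 36 + 16 = 52 months. Table 7-5 gives 60 months instead of 3 years, hence 60 to 76.

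**Model 1, all events captured.** All hazards are assumptions. Times are exponential, with rate a = ln 2 / (median time to progression), rate b = ln 2 / (median from progression to AML or death), and h = 0.01 per month for death before progression. The true curve is

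S(t) = exp(−(a+h)t) + [a/(a+h−b)] × [exp(−bt) − exp(−(a+h)t)].

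At 12 and 12 months, a = b = 0.05776, so S(24) = 0.1967 + 5.776 × (0.2500 − 0.1967) = 0.505.

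Simulated medians in months, stated rule against matching censoring (simulation error about 0.1 to 0.2):

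| Median to progression / then to AML or death | Matching | Stated rule, 12–36 mo follow-up | Stated rule, 36–52 mo follow-up |
|---|---|---|---|
| 6 / 6 | 13.2 | 12.3 (loss about 1) | 13.2 (loss about 0.1) |
| 9 / 9 | 19.0 | 16.5 (2.5) | 18.4 (0.6) |
| 12 / 12 | 24.3 | 20.1 (4.2) | 22.7 (1.6) |
| 9 / 18 | 27.3 | 19.6 (7.7) | 23.1 (4.2) |
| 18 / 18 | 33.3 | 26.2 (7.1) | 29.0 (4.3) |

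In the 12 / 12 case the stated rule gives 24-month EFS of 39% with 12–36 months of follow-up and 47% with 36–52, against a true value of about 50%. With 60–76 months the loss in the median is at most 1.8 months.

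**Model 2, other assumed hazards.** It uses 16-month uniform accrual, 8-week visits and separate transformation and death hazards after progression. The central case has medians of 12 months to progression, 12 from progression to death, 24 from progression to AML and 30 to an event without progression. The true median is 16.6 months.

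- All events captured: the stated rule gives 13.4 at a cut 6 months after last enrolment and 16.3 at 36 months. Across scenarios the loss is 1.3 to 5.7 months at the 6-month cut and 0 to 1.3 at 36 months.
- Transformations after progression not captured: the stated rule gives 14.4 at the 6-month cut (16.6 − 14.4 = 2.2 too low) but 18.4 at 36 months (18.4 − 16.6 = 1.8 too high). Across scenarios it is 0.9 to 3.5 too high at 36 months.
- Same setting, censoring at the last known alive date: 19.5, which is 19.5 − 16.6 = 2.9 too high.

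**The case against.** The strongest reply concerns size, direction and consequence.

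**Size.** The larger losses need immature data. They also need slow hazards: Section 1.5.1 puts median overall survival on hypomethylating agents at about 18 months, and EFS cannot exceed survival. Of the tabulated cases only 6 / 6 has a median EFS below that, and its loss at planned follow-up is about 0.1 month. This largely stands. However, the combination may do better than the historical figure. A regulatory submission could also draw on earlier data, and Section 3.7 allows the study to be ended early.

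**Direction.** A reader might infer that MDS EFS is biased downwards by months. The documents do not support that. They give no EFS hazards, and the downward effect is isolated only if every transformation is captured. Sections 7.6 and 7.7 do not secure that after progression or new therapy, and missed transformations push the curve up. This stands. Two opposing errors of unknown size still do not make a valid estimate.

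**Consequence.** EFS is descriptive, with no test, threshold or sample-size role. The formal test in Section 11.8.1.1 is on the complete remission rate. This stands and limits the weight of the point.

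Leaving detail to a statistical analysis plan is no answer, because the protocol itself fixes this rule.

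**Conclusion.** The censoring rule for MDS EFS is wrong as written: it does not match the event definition, and it discards event-free time after progression while counting deaths after progression. With all events captured it lowers the Kaplan-Meier curve or leaves it unchanged. Under the hazards assumed here the loss in the median is about 1 to 8 months with 12 to 36 months of follow-up, and about 0 to 4 months at the planned 3 years after last enrolment.

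These ranges rest on assumed exponential hazards, none of them from the protocol. The net direction is not established, because missed transformations act the other way and outweighed the censoring effect in the mature-data scenarios run without their capture. The point should be corrected, but it bears on a secondary endpoint only.

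**What to change.** In Section 10, give MDS EFS its own censoring sentence: patients without an event are censored at the last date they are known to be alive and free of AML transformation, irrespective of IWG progression. Keep the last progression-free date for PFS and AML EFS.

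In Section 7.7 and Table 7-5, add AML transformation status and date to the 2-month survival contacts for MDS patients, so that both the censoring date and later transformations are available. The last known alive date alone should not serve as a proxy, because it assumes freedom from AML that nobody has checked.

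The cost is one changed derivation and one extra question at contacts already scheduled.

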#### 11. STATISTICAL CONSIDERATIONS

The final analysis will be based on patient data collected through study discontinuation. The statistical analyses will be based on all patients who receive at least 1 dose of magrolimab. In general, data will be described and summarized as warranted by the sample size, and listings will be used in place of tables when the sample sizes are small. All summaries will be presented by indication (AML or MDS) and cohort (R/R or TN/U), and by treatment, when appropriate.

### 11.1. Safety Analysis

All patients who receive at least 1 dose of magrolimab will be included in the safety analysis.

The DLT analysis will be conducted in the TN/U Dose Evaluation Cohort in patients who completed either at least 4 infusions of magrolimab or 4 infusions/injections of azacitidine and have been followed for the 4-week DLT Assessment Period or have experienced a DLT within 4 weeks after initiating study drug treatment.

Safety will be assessed through summaries of deaths, DLTs, AEs, changes in laboratory test results, and exposure to magrolimab.

Adverse events leading to treatment discontinuation will be listed. AEs leading to the declaration of DLTs will be listed.

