## 3.3.2. TN/U Cohort Dose Evaluation

Dose evaluation will follow a 3+3 dose evaluation design. Up to 6 evaluable patients may be enrolled in each dose cohort. If none or 1 of the first 3 patients experiences a DLT, the cohort will be expanded to 6 patients. If 2 or more patients experience DLTs, the MTD dose level will have been exceeded, enrollment to that cohort will halt. CTSC will determine whether to treat additional patients at lower or higher dose levels or evaluate alternative dose regimens. The MTD for the TN/U Cohort is the maximum dose level at which at least 6 patients are treated with magrolimab and azacitidine and less than 34% of these patients experience a DLT. The RP2DS will be determined by the CTSC (Section 11.6) based on review of all available safety, efficacy, and PK data.

a. Azacitidine administered per region-specific labeling: SC in UK or US; IV in US only.

b. As of Amendment 6, all existing and newly enrolled TN/U cohort patients are to follow 30 mg/kg Q2W magrolimab dosing starting Cycle 3 and beyond.

Dose escalation/de-escalation and cohort expansion decisions will be reviewed and approved by the CTSC. Dose escalation or de-escalation may occur at dose increments or decrements, respectively, of up to 50% of the maximum prior dose as determined by the CTSC. The CTSC may add additional patients to any dose level to collect additional safety and PK information.

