## 3.3.4. TN/U Cohort Definition of DLT-evaluable Patients

Patients in the TN/U Dose Evaluation cohort are considered evaluable for assessment of DLT if EITHER of the following criteria are met during the DLT Assessment Period:

- The patient experienced a DLT at any time after initiation of the first infusion/injection of magrolimab.
- The patient completed at least 4 infusions of magrolimab and 4 infusions/injections of azacitidine.

For the TN/U Dose Evaluation cohort, patients who withdraw before completing the 4-week DLT Assessment Period for reasons other than a DLT, or who do not fulfill either of the criteria above, will not be evaluable for assessment of DLT for dose review decisions and will be replaced in the cohort.

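### Section 11.1 sets a wider DLT analysis set than the DLT-evaluable definition in Section 3.3.4, so a DLT proportion reported from it can only be equal or lower

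*Protocol*

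**What the plan says.** Two sections of the Protocol define which patients of the TN/U Dose Evaluation Cohort count when DLTs are assessed.

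- **Section 3.3.4** gives two routes. One is a DLT: "The patient experienced a DLT at any time after initiation of the first infusion/injection of magrolimab". The other is dosing: "The patient completed at least 4 infusions of magrolimab and 4 infusions/injections of azacitidine". Patients who meet neither route, or who leave before the end of the four weeks for a reason other than a DLT, "will not be evaluable for assessment of DLT for dose review decisions and will be replaced in the cohort".
- **Section 11.1** conducts the DLT analysis in "patients who completed either at least 4 infusions of magrolimab or 4 infusions/injections of azacitidine" who "have been followed for the 4-week DLT Assessment Period", or who "have experienced a DLT within 4 weeks after initiating study drug treatment".

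Section 3.3.2 supplies the dose-decision rules. A dose level qualifies as the MTD if at least six patients are treated and "less than 34% of these patients experience a DLT". The halting rule is a count: "If 2 or more patients experience DLTs, the MTD dose level will have been exceeded".

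**The concern.** The dosing route joins the two drugs with *and* in Section 3.3.4 and with *or* in Section 11.1. The follow-up condition in 11.1 adds time on study but no dosing requirement, so it does not close the gap. A patient can therefore be non-evaluable and replaced under 3.3.4, yet enter the DLT analysis under 11.1 as a patient without a DLT.

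The Protocol does not leave this to the SAP. Section 11.1 fixes the set itself, and an SAP or program written from it would carry the wider rule forward. At stake is whether the DLT summary reported for this cohort describes the same patients on whom the dose review rested, or a larger group that includes people who had too little of one drug to inform a judgement on the combination.

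**Working it through.** **Inputs**

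| Input | Value | Source in Protocol |
|---|---|---|
| Cycle 1 magrolimab, mg/kg | 1, 1, 15, 30, 30, 30 on Days 1, 4, 8, 11, 15, 22 | Table 3-2 |
| Azacitidine | daily, Days 1 to 7 | Table 3-2 |
| Maximum cohort size | 18 | Section 11.4 |
| Patients enrolled | 8, cohort closed | Section 11.4 |
| MTD limit | under 34%, at least six patients | Section 3.3.2 |

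**1. The Protocol's own figure.** Three dose levels of at most six patients give 3 × 6 = 18, as stated. The Protocol gives no DLT rate, power or error rate for this cohort, so there is nothing further to reproduce.

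**2. How the two sets relate.** Both sections require four weeks of observation for a DLT-free patient, and both count a patient with a DLT in that period whatever the exposure. The sets differ only in the dosing route. Anyone who meets *and* also meets *or*, so the 3.3.4 set lies inside the 11.1 set. The extra patients are all DLT-free.

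**3. Exposure of the extra patients.**
- Azacitidine route only: the fourth dose is due on Day 4. Scheduled magrolimab by then is 1 mg/kg, or 1 + 1 = 2 mg/kg.
- Magrolimab after four scheduled infusions: 1 + 1 + 15 + 30 = 47 mg/kg. All of Cycle 1: 47 + 30 + 30 = 107 mg/kg.
- Magrolimab route only: at least 47 mg/kg on schedule, including a 30 mg/kg dose, but fewer than four azacitidine doses.

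So the extra patients are under-exposed to one drug, and not always to magrolimab.

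**4. Direction.** With x DLTs among n patients in the 3.3.4 set and k extra patients, the proportions are x/n and x/(n + k). The second is never larger. With x = 0 both are zero.

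**5. Size, as an illustration.** Assume n = 6 and k = 1 or 2. The Protocol does not say how the eight patients divide.

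| DLTs | 3.3.4 set (n = 6) | 11.1 set, k = 1 | 11.1 set, k = 2 |
|---|---|---|---|
| 1 | 1/6 = 16.7% | 1/7 = 14.3% | 1/8 = 12.5% |
| 2 | 2/6 = 33.3% | 2/7 = 28.6% | 2/8 = 25.0% |

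**6. Thresholds.** Two DLTs in six is 33.3%, already under 34%. Three DLTs stay above it: 3/6 = 50.0%, 3/7 = 42.9%, 3/8 = 37.5%. With at least six evaluable patients and eight in total, the wider set does not move a result across the 34% line. Extra DLT-free patients cannot alter a rule that counts DLTs.

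**The case against.** The strongest reply is that nothing turns on the difference.

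- **Dose review has its own definition.** Section 3.3.4 says its criteria govern dose review and replacement, and the halting rule in 3.3.2 is a count. This stands. A reader might infer that the looser rule made the dose look safer when it was chosen. If the 11.1 set had filled the six slots, the probability of at most one DLT, at an assumed true rate of 33%, would rise from 0.358 to 0.468 with one under-exposed patient and 0.599 with two. But 3.3.4 excludes that use, so these figures do not describe the trial.
- **No cut-off is crossed.** A reader might see 33.3% falling to 25.0% as passing a 33% limit. The 33% figures belong elsewhere: to the low-risk MDS cohort in Sections 3.4 and 3.4.1, and to the interim safety review in Section 11.10, which does not name the TN/U Dose Evaluation Cohort.
- **Eight patients against six per dose level.** A reader might take the excess as proof that some patients met only the looser rule. The Protocol gives no reason for the number. Further dose levels, patients added by the CTSC (Section 3.3.2) and an early fourth patient (Section 3.3.3) were all possible.
- **The cohort is closed, the regimen is chosen, and DLTs will be listed individually.** This limits the harm. It does not remove the defect: Section 11 bases the final analysis on data through study discontinuation, and closing enrolment does not settle who is analysed.
- **A drafting slip.** Section 3.3.4 introduces its two routes with the word *either*, and 11.1 may be a garbled paraphrase. That is plausible but unproven. As written, 11.1 is a different rule that a programmer would implement.

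**Conclusion.** The two definitions contradict each other for the same cohort, and no other text in the Protocol resolves them. The consequence has a certain direction: any DLT proportion computed on the 11.1 set is equal to or lower than the one on the 3.3.4 set. Its size is unknown. Under the assumption of six patients meeting both conditions and two meeting only one, it is 16.7% − 12.5% = 4.2 percentage points for one DLT and 33.3% − 25.0% = 8.3 points for two. If every enrolled DLT-free patient met both conditions, or if there was no DLT, the reported proportion is unchanged.

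The finding is confined to the reported DLT analysis. The documents do not support a claim that the dose decision was affected, that a threshold was crossed, or that the added patients as a group never received the magrolimab dose under evaluation. Severity is low.

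**What to change.** Reconcile Section 11.1 with Section 3.3.4 so that the DLT analysis set is the DLT-evaluable set used for dose review. The simplest way is for 11.1 to refer to 3.3.4 instead of restating the criteria. List the remaining treated patients of the cohort separately, with their magrolimab and azacitidine exposure and their follow-up, so that none disappears from the report. Carry the same definition into any SAP text drawn from 11.1.

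The cost is one sentence in the Protocol and any matching SAP wording. No treatment, visit or sample size changes. The DLT denominator may become smaller if some enrolled patients met only one dosing condition; whether any did cannot be told from the Protocol.
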